6.2. Timing of Analyses

This study has 3 planned interim analyses, all of which were to be performed on cleaned, monitored and locked datasets. The first two interim analyses were to consider safety, reactogenicity, and immunogenicity data and to take place at the following time points:

- The first interim analysis would take place after the last subject in Group 1 had been followed through 28 days post-second ZPIV administration (Day 57) and the first interim database had been locked.
- The second interim analysis would take place after the last subject in Group 2 had been followed through 28 days post-second ZPIV administration (Day 57) and the second interim database had been locked.
- The third interim analysis would describe the incidence and severity of AFI/ARI after all subjects had completed one-year follow-up after the 2nd vaccination.

The second and third interim analyses were performed at the same time, thus two separate interim analyses occurred prior to the CSR, dated 12DEC2018 and 22DEC2020. The analyses performed for the interim analyses were described in a separate Statistical Analysis Plan, “Interim Statistical Analysis Plan for DMID Protocol: 16-0034 v1.0” dated 01OCT2018.

The final analysis will be presented in the Clinical Study Report which will occur after all safety and protocol-specified humoral immunogenicity results, including all primary and secondary endpoint data, collected through Day 750 are available and the database has been locked. Given the urgency to obtain data in a timely manner, additional humoral and cellular immunogenicity assessments could be summarized in one or more addenda to the main CSR.

6.3. Analysis Populations

Three analysis populations are defined: safety, immunogenicity, and per-protocol. In the case of mis-randomization or treatment administration error, subjects in all analysis populations will be analyzed according to the study vaccine received.

6.3.1. Safety Population

The Safety population will include all subjects who receive at least one study vaccination.

6.3.2. Immunogenicity (IMM) Population

The immunogenicity population will include all subjects who receive at least one study vaccination and contribute both pre- and at least one post-study vaccination sample for immunogenicity testing for which valid results are reported. Subjects with a loss of samples at pre-vaccination timepoints due to the natural disaster (i.e., Hurricane Maria) will be excluded from the GMFR and seroconversion analysis but will be included in post-baseline immunogenicity analyses where available. This population will be used for analysis of all immunogenicity data.

6.3.3. Per-Protocol (PP) Population

The Per Protocol (PP) population includes all subjects in the immunogenicity population with the following exclusions:

- Data from all available visits for subjects found to be ineligible at baseline.
- Data from all visits subsequent to major protocol deviations, such as:
 - Second vaccination not received,
 - Second vaccination received out of window,
 - Receipt of non-study licensed live vaccine within 30 days prior to or after each study vaccination,
 - Receipt of non-study licensed inactivated vaccine within 14 days prior to or after each study vaccination,
 - Receipt of immunosuppressive therapy (e.g., corticosteroids) within 30 days prior to or after each study vaccination.
- Data from any visit that occurs substantially out of window.

The Per Protocol population may differ across post-vaccination visits and denominators will be the number of samples tested and included in the analysis at each visit.

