## **15.6 Protocol Deviations**

A protocol deviation is any noncompliance with the study protocol, GCP, or protocol-specific MOP requirements. The noncompliance may be either on the part of the subject, the site principal investigator, or other study personnel. As a result of deviations, corrective actions are to be developed by the site and implemented promptly.

These practices are consistent with ICH E6:

- 4.5 Compliance with Protocol, Sections 4.5.1, 4.5.2, and 4.5.3
- 5.1 Quality Assurance and Quality Control, Section 5.1.1

---

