3. STUDY OBJECTIVES AND ENDPOINTS

3.1. Study Objectives

Primary Objectives:

1. Assess the safety and reactogenicity of a homologous prime boost regimen of ZPIV given at two different dose levels in a dose de-escalation format in healthy adult subjects who live in Puerto Rico, a flavivirus endemic area.
2. Compare the safety and reactogenicity profile of ZPIV after each vaccination, between dosage groups, and by pre-vaccination flavivirus immune status.

Secondary Objectives:

1. Assess the humoral immune response to a homologous prime-boost regimen of ZPIV after each dose of vaccine as determined by kinetics of the immune responses, seroconversion rates, and Geometric Mean Titers (GMT) overall, and compare results between dosage groups and by pre-vaccination flavivirus immune status.
2. Assess the durability of the humoral immune response to ZPIV at 6, 12, 18, and 24 months after the second vaccine administration overall, and compare results between dosage groups and by pre-vaccination flavivirus immune status.

Exploratory Objectives

1. Estimate the incidence of ZIKV and DENV infections between Visit 00 and the subject's last visit and describe the clinical presentation including disease severity overall, by dosage group, product received, and pre-vaccination flavivirus immune status.

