4.2. Discussion of Study Design, Including the Choice of Control Groups

The strategy for the initial development of this vaccine is to conduct a series of phase I studies to assess the safety and immunogenicity in flavivirus-naïve and flavivirus-experienced subjects. Because it is not known how previous exposure to flaviviruses will affect the safety and immunogenicity profile of this vaccine, this strategy will address a critical gap necessary to complete an early and rapid assessment of the viability of this ZIKV vaccine candidate. All trials will initiate with a 5 mcg dose. The first two clinical trials will explore the safety and immune response to the vaccine in flavivirus naïve subjects and in subjects that have been previously vaccinated with JEV or YFV vaccines. This trial will be conducted in Puerto Rico, whose population has been exposed to DENV 1-4, ZIKV and potentially YFV and/or WNV. A fourth clinical trial will be conducted by Beth Israel Deaconess Medical Center to evaluate the safety and immunogenicity of an accelerated vaccination schedule with the Zika vaccine candidate in healthy adults. The initial doses and regimens that will be utilized in these initial trials was selected based on experience with other inactivated flavivirus vaccines and recent data from mouse and NHP studies. Experience with licensed flavivirus vaccines suggests a 5 mcg dose should be safe and immunogenic; the 5 mcg dose was safe and protective in a NHP model [1]. Therefore, for these trials, subjects will be enrolled initially in the 5 mcg group. To determine if lower doses of ZPIV are equally or comparably immunogenic to the 5 mcg dose, subjects in this trial will then be enrolled in the 2.5 mcg group, or in a 1.25 mcg group in other trials. ZPIV is intended to be used in flavivirus endemic areas and among US military members and travelers who may have already received another flavivirus vaccine. Therefore, evaluating the safety and immune response in both flavivirus-naïve and flavivirus-immune subjects is important. This study provides the opportunity to evaluate ZPIV among a largely flavivirus-immune population who resides in an area with active ZIKV and DENV transmission.

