8.2. Secondary Immunogenicity Analyses

8.2.1. ZIKV Microneutralization Antibodies (MN50)

Seropositivity rates will be calculated based on ZIKV MN50 titers ≥ 10 and ≥ 100 . Seroconversion rates will be calculated based on the number of subjects experiencing at least a 4-fold rise in ZIKV MN50 titers from baseline.

Geometric mean titer (GMT) and 95% CI for ZIKV MN50 results at each visit and for peak titer results will be summarized by treatment group overall and by baseline flavivirus immune status for the immunogenicity (IMM) population in [Table 20](#) and per protocol (PP) population in [Table 21](#).

Geometric mean fold rise from baseline (GMFR) and 95% CI results at each post-baseline visit and for each subject's peak ZIKV MN50 titer results will be summarized by treatment group overall and by baseline flavivirus immune status for the IMM population in [Table 22](#) and PP population in [Table 23](#).

Seropositivity rates and 95% CIs at each visit and for peak ZIKV MN50 titer results will be summarized by treatment group overall and by baseline flavivirus immune status for the IMM population in [Table 24](#) and PP population in [Table 25](#).

Seroconversion rates and 95% CI at each post-baseline visit and using peak titer results will be presented by treatment group overall and by baseline flavivirus immune status for the IMM population in [Table 26](#) and PP population in [Table 27](#). Denominators for percentages will be the number of subjects with non-missing data at the applicable time point and 95% CI will be calculated using Clopper-Pearson methodology from a binomial distribution.

Graphical presentations of immune response by treatment group and baseline flavivirus immune status will include reverse cumulative distribution curves ([Figure 2](#) through [Figure 11](#) and longitudinal presentation of GMTs ([Figure 16](#) and [Figure 17](#)), seropositivity at a threshold of ≥ 10 ([Figure 18](#) and [Figure 19](#)), seropositivity at a threshold of ≥ 100 ([Figure 20](#) and [Figure 21](#)), and percent seroconversion ([Figure 22](#) and [Figure 23](#)).

A listing of ZIKV MN50 titers by subject, treatment group, baseline flavivirus immune status, planned time point, and actual study day is presented in [Listing 8](#).

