Per Protocol Population	Any Time Point								
	Any Reason								
	Found to be ineligible at baseline								
	Second vaccination not received ^b								
	Second vaccination received out of window ^b								
	Receipt of non-study licensed live vaccine within 30 days prior to or after study vaccination ^b								
	Receipt of non-study licensed inactivated vaccine within 14 days prior to or after study vaccination ^b								
	Receipt of immunosuppressive therapy (e.g., corticosteroids) within 30 days prior to or after study vaccination ^b								
	The visit occurred substantially out of window								
	Other major protocol deviation deemed exclusionary by study team								
	Prior to or at Day 1 visit (Visit 01):								
	Any Reason								
	Receipt of non-study licensed live vaccine within 30 days prior to or after study vaccination ^b								
	Receipt of non-study licensed inactivated vaccine within 14 days prior to or after study vaccination ^b								
	Receipt of immunosuppressive therapy (e.g., corticosteroids) within 30 days prior to or after study vaccination ^b								

Table 13: Analysis Populations by Treatment Group (continued)

		2.5 mcg ZPIV (N=X)		5 mcg ZPIV (N=X)		Placebo (N=X)		All Subjects (N=X)	
Analysis Populations	Reason Subjects Excluded	n	%	n	%	n	%	n	%
	Other major protocol deviation deemed exclusionary by study team								
	Prior to or at Day 15 visit (Visit 05):								
	Any Reason								
	Receipt of non-study licensed live vaccine within 30 days prior to or after study vaccination ^b								
	Receipt of non-study licensed inactivated vaccine within 14 days prior to or after study vaccination ^b								
	Receipt of immunosuppressive therapy (e.g., corticosteroids) within 30 days prior to or after study vaccination ^b								
	The visit occurred substantially out of window								
	Other major protocol deviation deemed exclusionary by study team								
	Prior to or at Day 29 visit (Visit 06):								
	Any Reason								
	Second vaccination not received ^b								
	Second vaccination received out of window ^b								
	Receipt of non-study licensed live vaccine within 30 days prior to or after study vaccination ^b								
	Receipt of non-study licensed inactivated vaccine within 14 days prior to or after study vaccination ^b								
	Receipt of immunosuppressive therapy (e.g., corticosteroids) within 30 days prior to or after study vaccination ^b								
	The visit occurred substantially out of window								

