14.2 Immunogenicity Data

ZIKV Microneutralization Titers

Table 20: ZIKV Microneutralization Antibody (MN50) Geometric Mean Titer (GMT) Results with 95% Confidence Intervals by Time Point, Treatment Group, and Baseline Flavivirus Immune Status – Immunogenicity Population

[Implementation note: If a baseline flavivirus subgroup includes fewer than 2 subjects, the GMT and 95% CI fields will be populated with 'N/A'.]

Time Point	Baseline Flavivirus Immune Status	2.5 mcg ZPIV			5 mcg ZPIV			Placebo		
		n	GMT	95% CI	n	GMT	95% CI	n	GMT	95% CI
Baseline	All Subjects	x	xx	xx.x, xx.x	x	xx	xx.x, xx.x	x	xx	xx.x, xx.x
	Baseline ZIKV Seropositive									
	Baseline ZIKV Seronegative									
	Baseline ZIKV Seropositive and DENV Seropositive									
	Baseline ZIKV Seropositive and DENV Seronegative									
	Baseline ZIKV Seronegative and DENV Seropositive									
	Baseline ZIKV Seronegative and DENV Seronegative									

Repeat Baseline for:

Day 29 (Pre-Dose 2)										
Day 57 (28 Days Post-Dose 2)										
Day 209 (180 Days Post-Dose 2)										
Day 750 (721 Days Post-Dose 2)										
Peak Post-Baseline										

n = Number of subjects in the immunogenicity population with non-missing immunogenicity data at the specified time point.

95% CI = 95% confidence interval based on Student's t-distribution.

Table 21: ZIKV Microneutralization Antibody (MN50) Geometric Mean Titer (GMT) Results with 95% Confidence Intervals by Time Point, Treatment Group, and Baseline Flavivirus Immune Status – Per Protocol Population

Table 22: ZIKV Microneutralization Antibody (MN50) Geometric Mean Fold Rise (GMFR) Results with 95% Confidence Intervals by Time Point, Treatment Group, and Baseline Flavivirus Immune Status – Immunogenicity Population

[Implementation note: baseline results are not included in this table.]

Table 23: ZIKV Microneutralization Antibody (MN50) Geometric Mean Fold Rise (GMFR) Results with 95% Confidence Intervals by Time Point, Treatment Group, and Baseline Flavivirus Immune Status – Per Protocol Population

[Implementation note: baseline results are not included in this table.]

Table 24: ZIKV Microneutralization Antibody (MN50) Seropositivity Results with 95% Confidence Intervals by Time Point, Treatment Group, and Baseline Flavivirus Immune Status – Immunogenicity Population

[Implementation note: If a baseline flavivirus subgroup includes fewer than 2 subjects, the % and 95% CI fields will be populated with 'N/A'.]

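### No rule covers ZIKV titres drawn after a confirmed natural ZIKV or DENV infection, so late and peak results can credit infection-induced antibody to ZPIV

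*SAP*

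**What the plan says.** The second secondary objective in SAP 3.1 is to "Assess the durability of the humoral immune response to ZPIV at 6, 12, 18, and 24 months after the second vaccine administration overall". SAP 4.2 describes the site as "an area with active ZIKV and DENV transmission", and follow-up runs for 24 months after the boost.

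SAP 8.2.1 states: "Geometric mean titer (GMT) and 95% CI for ZIKV MN50 results at each visit and for peak titer results will be summarized by treatment group". It adds GMFR, seropositivity and seroconversion, each for the immunogenicity (IMM) and PP populations and by baseline serostatus. SAP 8.2.2 repeats this for ELISA. The table shells in SAP 14.2 include a row labelled "Peak Post-Baseline", with no latest visit.

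SAP 6.3.2 says of IMM: "This population will be used for analysis of all immunogenicity data". SAP 6.3.3 then takes three kinds of data out of PP: all visits of subjects ineligible at baseline, visits substantially out of window, and "Data from all visits subsequent to major protocol deviations, such as" a missed or late second dose, a non-study vaccine or immunosuppressive therapy. Protocol 11.4.1 has the same list. The Table 13 shell adds a catch-all: "Other major protocol deviation deemed exclusionary by study team".

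Confirmed infection is defined in SAP 3.3. It requires an acute febrile or rash illness (AFI/ARI) with either a positive PCR within 14 days of onset or a 4-fold rise in ZIKV or DENV neutralization titre across the illness visit. That status is used in the AFI/ARI summaries of SAP 9.9 and in the listings, but not in the immunogenicity tables.

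**The concern.** The durability objective concerns the response to ZPIV. A subject who has a natural ZIKV infection between Day 57 and Day 750 may have later titres that reflect the infection. Under the plan those titres enter the visit GMT and GMFR as persistence, can turn a non-responder into a seroconverter, and can become that subject's peak. The overlap is direct: a 4-fold rise in ZIKV MN50 is one way to confirm infection, and a 4-fold rise from baseline in the same assay is seroconversion. One titre can therefore count as both.

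At stake is how the late results are read, chiefly in the baseline-serostatus strata. SAP 6.4 allows these to be displayed with as few as two subjects.

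**Working it through.** **1. Is there any route by which such titres are set aside?**

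- The PP list is open-ended, but only for protocol deviations. Protocol 15.6 defines these: "A protocol deviation is any noncompliance with the study protocol, GCP, or protocol-specific MOP requirements". A mosquito-borne infection is not noncompliance.
- The Table 13 catch-all is also limited to deviations, and it is discretionary.
- The outlier rule in Protocol 11.4.5 covers points that look erroneous or cannot be explained. A rise after a confirmed infection can be explained.
- SAP 8.2.1 and 8.2.2 contain no flag, no censoring and no infection-based sensitivity analysis.

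No route exists.

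**2. The plan's own figures.** The documents give no infection figure. The only related figures are the probabilities of at least one event in SAP Tables 8 and 9 (Protocol Tables 3a and 3b), from 1 − (1 − p)^n:

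- n = 35, p = 5%: 1 − 0.95^35 = 83.4% (stated 83.4%).
- n = 80, p = 2%: 1 − 0.98^80 = 80.1% (stated 80.1%).
- Rate detectable with 80% power, 1 − 0.20^(1/n): 4.49% for n = 35 and 1.99% for n = 80 (stated 4.5% and 2.0%).

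These reproduce.

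**3. Chance of at least one infected subject.** Same formula. Protocol 11.2 gives about 35 evaluable ZPIV subjects per dose and 5 placebo per group (10 pooled). The attack rates are assumptions.

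| Assumed attack rate | ZPIV arm, n = 35 | Pooled placebo, n = 10 |
|---|---|---|
| 3% | 66% | 26% |
| 5% | 83% | 40% |
| 10% | 97% | 65% |

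**4. Effect on the GMT.** If k of n titres are multiplied by F, the geometric mean is multiplied by F^(k/n). F is an assumption, and so is the stratum of 10.

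| Infected / n | F = 10 | F = 50 |
|---|---|---|
| 1 / 35 | 10^(1/35) = 1.07 | 50^(1/35) = 1.12 |
| 1 / 10 | 10^(1/10) = 1.26 | 50^(1/10) = 1.48 |

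Over a wider assumed range of F = 4 to 100 at n = 35, one infection gives 1.04 to 1.14 and four give 1.17 to 1.69. The GMFR takes the same factor, because the baseline titre precedes the infection. For the peak, F is the ratio to the subject's own earlier peak, so there is no effect when the post-infection titre is lower.

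**5. Effect on seroconversion.** At most k/n: one subject who had not otherwise seroconverted adds 1/35 = 2.9 percentage points, or 1/10 = 10 points in a stratum of 10.

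**6. Scale.** With an assumed log10 SD of 0.4 to 0.6, the 95% CI of a GMT extends by 10^(t × SD/√n): a factor of 1.37 to 1.61 at n = 35 and 1.93 to 2.69 at n = 10.

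**The case against.** The strongest reply is that PP, as written, is internally consistent. It is defined by eligibility, dosing, prohibited products and visit windows, and infection is none of these. A reader might infer that PP exists to show a response free of outside influence, and so is wrongly defined. Neither document states that purpose. Wanting an infection-free summary is a choice of estimand. This stands, and it is why the population definitions should not be changed.

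The affected titres can also be found. Listing 8 gives every titre by study day. Listing 12 gives illness start, PCR results, flanking visits and 4-fold rises. Tables 147 to 153 count confirmed infections by arm. That helps a careful reader, but it is not an analysis. The placebo column shares the exposure, but with about 10 subjects it is a weak guide: even 0 of 10 infected has an exact 95% upper limit of 31%. No placebo-adjusted titre contrast is planned.

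On size, every single-infection factor in step 4 lies inside the CI range in step 6, and the study is descriptive and exploratory. This also stands, although a shift in one direction is not made harmless by a wide interval.

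Finally, excluding such titres from PP itself would have costs of its own. It would put the SAP out of line with Protocol 11.4.1. It would partly select on the endpoint assay. It would also come after an interim report dated 22DEC2020 that combined the second and third planned analyses, with interim results available to the study team. A labelled sensitivity analysis avoids most of this.

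**Conclusion.** The omission is real. No rule in SAP 6.3.3, SAP 8.2 or Protocol 11.4.1 deals with titres after a confirmed infection, and the peak has no cut-off. Late GMT, GMFR, seroconversion and peak results can therefore include infection-induced antibody.

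The size cannot be derived from the documents. One infection under an assumed 10- to 50-fold rise gives 1.07 to 1.12 times in an arm of about 35, which is small, and 1.26 to 1.48 times in an assumed stratum of 10, which could change how that stratum is read.

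A reader might go further and infer that the durability results will be materially biased. The documents do not support that: they give no attack rate and no post-infection rise. Nor do they say how far a DENV infection raises ZIKV titres, so the DENV part of the point is weaker than the ZIKV part. This is a cheap improvement to a secondary, descriptive analysis.

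**What to change.** Leave the IMM and PP definitions unchanged in both documents. Add to SAP 8.2.1 and 8.2.2 a labelled sensitivity analysis, in all arms:

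- Repeat the PP GMT, GMFR, seroconversion and peak results with titres censored from the onset of an infection confirmed under SAP 3.3.
- Where confirmation rests only on a 4-fold ZIKV titre rise, count it for censoring only if the earlier flanking sample was drawn on or after Day 57, so that a vaccine response is not taken for infection. The limit must include Day 57 itself. Protocol Table 2 schedules the next serum for humoral immunity at Day 209, so a limit of strictly after Day 57 would leave illnesses in between with no way to be confirmed by titre.
- Show the same results censoring on PCR-confirmed infection alone, because a ZIKV titre criterion selects on the endpoint assay.
- Use illness data to the last visit. Many AFI/ARI table shells are titled through 12 months after the final vaccination, but Protocol 9.4 collects these illnesses to the end of the study.

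The data are already in Listings 8 and 12, so the cost is a paragraph of SAP text, a date filter and some extra tables. A few late titres drop out of the sensitivity analysis. Infections without AFI/ARI remain undetected, and a ZIKV infection shown only by a titre rise from a sample before Day 57 is not censored. The bias is reduced, not removed. Because interim results have been reported, the analysis should be described as added after them.
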